Primary Objective:	
 - To describe when urinary hormones (follicle stimulating hormone and luteinising hormone) start to raise and when they reach their peak among male preterm neonates born with a gestational age <32 weeks. - To investigate if there is a difference in hormone levels and their peak timing between extremely preterm babies (<28 weeks of gestational age) and very preterm babies (28-32 weeks of gestational age).
Secondary Objective:	
 - Identify a link between hormone levels and linear growth in the first months of life in preterm neonates. - Identify a link between hormone levels and the development of external genitalia (testicular volume and position, penile length). - Identify a link between hormone levels and short-term neurocognitive development.
Rationale:	The knowledge about the activation of the hypothalamic-pituitary-gonadal axis (HPG) in the first months of life is relatively recent. It is scientifically proven that in this period, called "minipuberty", there is the same activation that occurs during puberty. This is responsible for changes in terms of growth, pubertal development and neurobehavioral patterns. Understanding all the factors involved in children's physical and neurocognitive development has a significant scientific impact and could provide useful information in case of future problems. As prematurity survival rates continue to improve, clinicians need to be familiar with the hormonal changes in these patients and the first months of life provide a 'window of opportunity' for functional studies of the HPG axis prior to pubertal development
Methodology:	This is a preliminary prospective and cross-sectional study.
Sample Size:	20 male preterm neonates with a gestational age ≤ 32 weeks
Main Inclusion Criteria:	
 • Male preterm infants born ≤ 32 weeks of gestational age • Written informed consent provided
Main Exclusion Criteria:	
 • Female sex assignment at birth • Male preterm infants born >32 weeks of gestational age • Male infants born at term
Statistical Analysis:	Results shall be expressed as median (range) and analysed using Minitab. Some data may require log transformation. Pearson's correlation shall be used for univariate analysis of association of and multivariate analysis shall be performed using backward stepwise linear regression analysis including factors significant from univariate analysis (Pearson's

	correlation) as independent factors. The Mann Whitney U test shall be used for comparison of nonparametric data. Statistical significance shall be set at $p < 0.05$.
--	--

Full title: PRELIMINARY STUDY ON ACTIVATION OF THE HYPOTHALAMIC-PITUITARY-GONADAL AXIS IN INFANCY (MINIPUBERTY) AND ITS EFFECTS ON CATCH-UP GROWTH AND NEUROCOGNITIVE OUTCOME IN MALE PRETERM NEONATES BORN AT <32 WEEKS OF GESTATIONAL AGE

Short title: Minipuberty and its effects on preterm neonates

1. Introduction

The activation of the hypothalamic-pituitary-gonadal axis (HPG) develops through three main moments: foetal life, first postnatal months (usually first 6 months of life) and finally during puberty.¹ During the foetal period, there is a peak of gonadotropin secretion starting from the second trimester of gestation, and a subsequent suppression in the last weeks until birth, due to the negative feedback of placental estrogens.² In male foetuses, LH levels exceed those of FSH. The foetal testis secretes testosterone and anti-müllerian hormone (AMH) from the 8th week of gestation and this is essential for masculinization. Formation of the active metabolite of testosterone, dihydrotestosterone, is required for the development of the prostate, penis and scrotum.³ Initial testicular development is intra-abdominal and the descent of the testes into the scrotum occurs in two phases. The first, transabdominal, phase is completed by 15 weeks of gestation. The second, inguinoscrotal, phase is usually completed by the end of the 35th week of gestation and this phase is androgen dependent. Testosterone levels are high in male foetuses between 10 and 20 weeks of gestational age, reaching adult values, and decrease thereafter towards term.⁴ In the same way LH and FSH levels decrease towards the end of gestation and are low at term in both sexes, due to the negative feedback of placental oestrogens.

A second post-natal HPG activation, also called "minipuberty", occurs at around 1 week of age, when placental hormones are cleared from the circulation. From the first weeks of life onwards there is a progressive increase in gonadotropins levels with a greater increase of FSH in females and of LH in males. During the "minipuberty" period gonadotropins levels have a peak at 3 months of life and a progressive exhaustion at around 6 months, except for FSH levels in females that can remain high even up to 3 or 4 years. Particularly in males, testosterone and androgen levels are associated with development and maturation of the reproductive system (penis and testis) as well as the androgynous cutaneous manifestations and a different neurobehavioral structure.⁵ Postnatal testosterone levels have been associated with male-type behaviour in 14-month-old infants, suggesting a role in neurobehavioral development.⁶ Recently, it has also been suggested how the increasing testosterone level during the first 6 months of life, as well as during puberty, translates into an increase of linear growth, regardless of the levels of growth hormone (GH) or insulin-like growth factor (IGF1).⁷ Preterm birth does not seem to influence post-natal HPG activation, since that gonadotropin levels seem to raise up at the same time as term infants after the birth. The difference is that in preterm neonates these values last higher and longer than full-term newborns. According to the most recent longitudinal data, the post-natal activity of this axis declines at about the same in term neonates compared to premature infants with the same corrected gestational age, suggesting that the HPG activity is evolutionarily regulated.^{8,9} This higher increase of gonadotropin levels in premature males has been associated with a faster penile and testicular growth after birth compared to full-term boys. At last, in neonates small for gestational age (SGA) there are some evidence that post-natal FSH and testosterone levels are higher compared to infants with an adequate weight (AGA), although it is not known

whether this correlates or have any influence on the catch-up growth of this subjects.^{10,11} Understanding how “minipuberty” can influence linear growth, genitalia development and neurocognitive processes in preterm neonates has a significant scientific impact and could provide us more information in understanding auxological and neurobehavioral developmental patterns of this population.

2. Aim/Primary and Secondary Objectives

This is a preliminary prospective and crosssectional study aiming to describe “minipuberty” in male preterm children at the Royal Hospital for Children in Glasgow. The research project has been discussed by the Developmental Endocrinology Research Group at the University of Glasgow.

- **Primary Endpoint**

- To describe when urinary hormones (follicle stimulating hormone and luteinising hormone) start to raise and when they reach their peak among male preterm neonates born with a gestational age <32 weeks.
- To investigate if there is a difference in hormone levels and their peak timing between extremely preterm babies (<28 weeks of gestational age) and very preterm babies (28-32 weeks of gestational age).

- **Secondary endpoints**

- Identify a link between hormone levels and linear growth in the first months of life in preterm neonates.
- Identify a link between hormone levels and the development of external genitalia (testicular volume and position, penile length).
- Identify a link between hormone levels and short-term neurocognitive development.

3. Study Design

This is a preliminary prospective and cross-sectional study on male preterm children at the Royal Hospital for Children in Glasgow. The study will not include any investigational medical product. The research project has been discussed by the Developmental Endocrinology Research Group at the University of Glasgow.

This study will be performed according to the Research Governance Framework for Health and Community Care (Second edition, 2006).

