3.5 Withdrawal of subjects

Participants have the right to withdraw from the study at any point for any reason.

4 Study Outcome Measures

Our study will include 3 types of different evaluations on each neonate:

- Multiple urine collections to evaluate urinary gonadotrophin levels
- Multiple clinical evaluations of auxological parameters and external genitalia
- Neurocognitive assessment at 3 months of corrected gestational age

Timing of sample analysis and simultaneously clinical evaluation will be as follow:

T1: 1-3 days of life

T2: 7 days of life

T2a – T2z: one per week until 40 weeks of post-conceptual age or until discharge from Neonatal Unit

T3-TX: urinary sample analysis and clinical evaluation during the routine follow up clinics until 12 months of corrected gestational age

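### Hormone level is to be linked to testis position with no age term and no rule on which hormone value counts, so a visit-level analysis would find a link from the passage of time alone

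*Combined protocol and SAP*

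**What the plan says.** Section 2 gives as a secondary endpoint: "Identify a link between hormone levels and the development of external genitalia (testicular volume and position, penile length". It does not say whether the hormone level is the concurrent value, an earlier one, a mean or the peak.

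Section 4 schedules urine sampling and clinical evaluation together: at days 1-3, at day 7, then "one per week until 40 weeks of post-conceptual age or until discharge from Neonatal Unit", then at follow-up clinics to 12 months corrected age. Section 4.2 places the genital examination at the moment the urine bag is fitted. It gives no scale for testis position.

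Section 6 (repeated in the synopsis) names Pearson correlation, backward stepwise linear regression on the factors significant in that step, and the Mann-Whitney test. It names no adjustment for postnatal or postmenstrual age and no model for repeated visits.

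The Introduction supplies the timings. The inguinoscrotal phase of descent "is usually completed by the end of the 35th week of gestation and this phase is androgen dependent". Postnatal activation "occurs at around 1 week of age". "From the first weeks of life onwards there is a progressive increase in gonadotropins levels", and "gonadotropins levels have a peak at 3 months of life". In preterm infants "gonadotropin levels seem to raise up at the same time as term infants after the birth".

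**The concern.** Testis position follows a developmental timetable that the protocol counts in weeks of gestation. The hormones follow one that it counts from birth. Over the weekly visits both move in one general direction: hormone levels up, testes down. If paired visits are correlated without age, they will correlate whether or not the hormones affect descent.

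Position also has an end point that length and weight lack: once both testes are in the scrotum, there is no further descent to explain. A hormone value taken after that examination cannot be read as a cause of it. The plan sets no rule to keep such values out.

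At stake is the testis-position part of one secondary endpoint. A significant result could be reported as an effect of minipuberty when it shows only that the infants grew older.

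**Working it through.** The plan gives no power, effect size or expected correlation for this endpoint, so there is no figure to reproduce.

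**Step 1: one clock.** From the documents: descent usually complete by week 35, activation at 1 week of age, peak at 3 months, visits as in section 4. Assumed: 3 months = 13 weeks; births from 24 weeks (the protocol gives no lower limit); the fetal timetable applied to infants already born.

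- Activation = birth age + 1
- Paired visits up to 35 weeks = 1 + (35 − birth age), that is, the first visit plus one per completed week; fewer if discharge comes sooner
- Peak = birth age + 13

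| Birth (weeks) | Activation | Weeks before 35 | Paired visits to week 35 | Peak | Weeks after 35 |
|---|---|---|---|---|---|
| 24 | 25 | 10 | 12 | 37 | 2 |
| 28 | 29 | 6 | 8 | 41 | 6 |
| 32 | 33 | 2 | 4 | 45 | 10 |

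The peak falls as early as week 35 only for birth at 35 − 13 = 22 weeks. Samples before week 35 are nonetheless scheduled for every infant.

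**Step 2: what time alone produces.** Simulation with no hormone effect on descent, 1,000 trials per row. From the documents: 20 infants, weekly visits to 40 weeks, a rise from week 1 to week 13. Assumed: birth age uniform over 24-32 weeks, log hormone rising linearly, SD 0.5 between and 0.5 within infants, descent at mean 35 weeks with SD 1.5. The analysis is pooled visit-level Pearson correlation of log hormone with position (descended or not).

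| Rise (log units) | Fold rise = exp(rise) | Mean r | p < 0.05 |
|---|---|---|---|
| 0 | 1 | 0.00 | 5% |
| 0.5 | 1.6 | 0.16 | 68% |
| 1 | 2.7 | 0.28 | 99% |
| 1.5 | 4.5 | 0.39 | 100% |
| 2 | 7.4 | 0.46 | 100% |

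A separate run for 2- to 10-fold rises gave 87-100%.

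**Step 3: does handling the repeated visits cure it?** Births at 25-32 weeks, descent at mean 34 weeks with SD 1 or 2, log SD 0.5 between and 0.4 within infants (all assumed). A within-infant comparison of visits before and after descent, without age, was falsely significant in 88-92% of trials for a 1.5-fold rise and over 99% for 2- to 10-fold rises. Adding postnatal age brought this to 4-7%, and to 4-8% over all the settings tried. So age is needed as well as a repeated-measures model.

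**Step 4: one value per infant.** Peak hormone against age at descent was falsely significant in 4-6% of trials, close to nominal. Mean hormone against postnatal age at descent gave 5-7%, 12-16% and 18-26% for 2-, 5- and 10-fold rises. Mean hormone over day 7 to week 3 against postmenstrual age at descent, adjusted for birth age, gave 3-6%.

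**The case against.** A reader might infer that the plan relates descent to hormone values measured afterwards, and that hormones after week 35 cannot have influenced it. The documents do not support either statement. Nothing makes the peak or a later value the exposure for testis position, and step 1 shows 4 to 12 paired visits scheduled by week 35. The protocol says descent is usually, not always, complete by then, and it describes a timetable in utero. In an infant still undescended later, later hormone values do precede descent. The 3-month peak is also a general figure: the Introduction says that "in preterm neonates these values last higher and longer than full-term newborns", and peak timing in these infants is part of the primary endpoint.

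It can also be said that section 6 never states that visits will be pooled, that the simulated rates rest on assumed inputs, and that one peak value per infant against age at descent keeps its error rate. All of that stands. The 70-100% applies to an unadjusted visit-level analysis, which the paired schedule invites and the plan does not rule out. With a single peak value the difficulty is the order in time, not false positives.

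Finally, one age term removes most of the problem, and the same omission affects length, weight, penile length and testicular volume. That is true, and the age adjustment can be written once for all of them. Particular to position is the need to exclude hormone values taken after descent. The study is small and preliminary, which limits the severity but does not make a near-certain spurious link acceptable.

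**Conclusion.** The point holds as an undefined exposure combined with a missing age adjustment. Applied to the paired visits without age, the stated methods would show a hormone-position link from time alone in about 70-100% of trials for assumed 1.6- to 10-fold rises, against about 4-8% with postnatal age in a within-infant model. The direction follows from the protocol's own timings. The size depends on the assumed rise, SDs and spread of descent, none of which the documents give.

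The order-in-time part is conditional: if the 3-month peak were the exposure, it would usually follow descent, by 2 to 10 weeks for births at 24 to 32 weeks. The plan leaves that open. The change should be made, in proportion to one part of a secondary endpoint.

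**What to change.** For testis position, state how position is scored and choose one of two analyses.

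1. **Age at descent.** The outcome is postmenstrual age at the first examination with both testes in the scrotum, censored if not reached. Use only log LH and FSH measured before that examination, with gestational age at birth in the model. Enter the most recent earlier value, updated at each visit. A mean of everything up to descent would bring the time trend back, because late descenders contribute more of the later, higher values.
2. **Within-infant model.** A repeated-measures model of position on the concurrent or preceding log LH and FSH, with postnatal age included. Let the age term curve: in the linear-rise simulations a straight-line term removes the trend by construction, and the real rise may not be linear.

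Under either, state that peak and post-descent hormone values will not be interpreted as influencing descent. A fixed early window is optional. If day 7 to week 3 were used, about 15-20% of infants would have fewer than three eligible samples and 1-6% none under the assumed descent timing, so those infants should be reported.

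The cost is wording only, since all the data are already scheduled. The downside is fewer usable samples in infants born near 32 weeks and less precision. With one value per infant, N = 20 needs |r| of at least 0.44 for p < 0.05 and a true r of about 0.59 for 80% power, so the result should be labelled exploratory.

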4.1 Primary Outcome Measure

Urine collection will be done with a plastic bag with a sticky strip on one end, made to fit over baby's genital area. In extremely preterm babies (<28 weeks of gestational age) urine collection will be from cotton wool in the nappy because of their sensitive skin.

Samples will be analyzed on fresh urine for urinary gonadotropin levels (FSH, LH) as detailed in laboratory tests section.

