4.2. Secondary Outcome Measure

- Auxological parameters for each evaluation will include: length, weight, head circumference. They are routinely checked both during the baby's hospital stay and the routine follow-up clinics therefore we will not add any to the standard baby's care.
- External genitalia evaluation will include: testicular volume and position, penile length. This is not a part of the routine monitoring of preterm babies but it is not invasive and it will be done at the same time of plastic bag's positioning for urine collection in order to minimize handling of the baby.
- Short term neurocognitive outcome: during the hospital stay in the Neonatal Unit parents will be asked if they agree with video recording their baby using their mobile phone at home after discharge. We would like to assess the Fidgety Movements at 3 months of corrected gestational age using the Prechtl's method^{12,13}. If the parents agree, we will give an instruction sheet before they go home briefly explaining how they have to record their baby and for how long. Fidgety Movements are a spontaneous pattern of movements which parents can record without the need for a healthcare professional. Parents will upload their videos onto a secure video messaging system (www.vcreate.tv) which already has governance approval in GGC and is endorsed by the NHS. [name] is an Italian researcher at the University Hospital of Modena (Italy). She is a highly trained expert of Prechtl's Method and a member of the General Movements Trust. With an expert team she will review all the videos giving an evaluation of the Fidgety Movements pattern. We will

store the videos for a maximum of 10 years and will delete them after this time.

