4.3 Laboratory Tests

Measurement of LH and FSH urinary levels will be made on fresh samples using electro-chemiluminescence immunoassay (ECLIA). Sample analysis will be performed by the Biochemistry Department of the Royal Hospital for Children in Glasgow using Abbott Architect i1600 instrument.

5. Assessment of Safety

We do not expect particular problems in this study. Urine collection will be made in the same way of routine collection in infants. Auxological evaluations are part of the routine care of preterm neonates and we will add a non-invasive evaluation of external genitalia without particular risks for the babies. Neurobehavioural development will be evaluated using parents' video only if they agree with video recording their baby. This will allow parents to stay at home without bringing their baby to the hospital.

6. Statistics and Data Analysis

Results shall be expressed as median (range) and analysed using Minitab. Some data may require log transformation. Pearson's correlation shall be used for univariate analysis of association of and multivariate analysis shall be performed using backward stepwise linear regression analysis including factors significant from univariate analysis (Pearson's correlation) as independent factors. The Mann Whitney U test shall be used for comparison of nonparametric data. Statistical significance shall be set at $p < 0.05$.

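### Birth size is neither named as a factor nor adjusted for in the hormone-growth analysis, so an FSH-growth correlation could reflect birth size rather than the hormone

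*Combined protocol and SAP*

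**What the plan says.** The Introduction reports that "in neonates small for gestational age (SGA) there are some evidence that post-natal FSH and testosterone levels are higher" than in infants of adequate weight. It adds that it is not known "whether this correlates or have any influence on the catch-up growth of this subjects". The full title names effects on catch-up growth, and one secondary endpoint in Section 2 is: "Identify a link between hormone levels and linear growth in the first months of life in preterm neonates".

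SGA and birth size do not appear again after the Introduction. Sections 3.2 and 3.3 select on sex, gestational age and consent only, so SGA infants can be enrolled. Section 4.2 lists the growth measurements ("Auxological parameters for each evaluation will include: length, weight, head circumference"), taken from T1 at 1-3 days of life, but no size-for-gestation variable and no growth reference. The hormones assayed are FSH and LH (Sections 4.1 and 4.3).

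Section 6, repeated in the synopsis, plans univariate Pearson correlations and then "backward stepwise linear regression analysis including factors significant from univariate analysis", with significance at 0.05. It lists no candidate factors and forces none into the model.

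**The concern.** The protocol itself raises the possibility that birth size is tied to one of the two measured hormones. If birth size is also tied to how fast an infant grows, the two links together produce an FSH-growth correlation even when FSH has no effect on growth. Expressing growth relative to age would not remove this, because the difference lies between infants rather than along the age trend.

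At stake is how the growth objective is read. A positive FSH-growth correlation could not be told apart from SGA infants having both higher FSH and faster growth. That leaves unanswered the question the Introduction describes as open.

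**Working it through.** The plan gives no power calculation, effect size or standard deviation for this analysis, so there is no planned figure to reproduce. The check asks how often an unadjusted FSH-growth correlation would be significant if birth size were the only source of it.

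**Inputs from the documents.** n = 20 (Section 3.1); significance level 0.05 (Section 6; taken as two-sided, which the plan does not state).

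**Assumed inputs, not in the documents.** SGA share p = 20% or 30%; SGA shifts log FSH by a SD and growth by b SD; no direct effect of FSH on growth.

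**Step 1: size of correlation needed.** With 18 degrees of freedom the critical t is 2.101, so the critical |r| is 2.101 / √(18 + 2.101²) = 0.444.

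**Step 2: correlation induced by SGA alone.** For a binary SGA status and a = b = d,

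r = p(1−p)d² / [1 + p(1−p)d²].

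- d = 0.5: 0.04/1.04 = 0.038 (p = 20%); 0.0525/1.0525 = 0.050 (p = 30%)
- d = 1: 0.16/1.16 = 0.138; 0.21/1.21 = 0.174
- d = 1.5: 0.36/1.36 = 0.265; 0.4725/1.4725 = 0.321
- If b = 0, r = 0.

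**Step 3: false-positive rates.** 40,000 simulated studies of 20 infants per scenario, with 4 or 6 SGA infants. Each cell gives the result for p = 20% / 30%.

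| SGA shift in FSH, growth (SD) | Unadjusted Pearson | Screen admits SGA, if offered | Hormone falsely kept after screen and backward elimination, SGA offered | Hormone significant with SGA forced in |
|---|---|---|---|---|
| 0.5, 0.5 | 5.2% / 5.4% | 13.7% / 16.9% | 4.8% / 4.8% | 5.0% / 5.0% |
| 1, 0 | 5.1% / 4.9% | 5.0% / 4.9% | 4.8% / 4.5% | 5.1% / 4.9% |
| 1, 1 | 9.1% / 11.5% | 39.2% / 49.4% | 5.6% / 6.0% | 4.8% / 4.9% |
| 1.5, 1.5 | 21.4% / 30.2% | 71.9% / 82.7% | 7.1% / 7.0% | 5.2% / 5.0% |

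If the number of SGA infants varies by chance around the same share, the unadjusted rates are 8.9% / 10.9% at 1 SD and 20.7% / 28.6% at 1.5 SD. I quote these rounded, as 9-11% and 21-29%; the fixed-count figures lie within two percentage points of them.

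**Step 4: where the excess comes from.** The Unadjusted column describes two situations that the plan allows: the univariate Pearson result reported by itself, and a stepwise model in which birth size was never a candidate. Once birth size is a candidate, most of the excess goes.

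**The case against.** The best defence is that the two-step procedure deals with this by itself. If birth size were a candidate, the screen would usually admit it when its effect is large (72-83% of studies at 1.5 SD), and the hormone term would be falsely kept in only about 5-7%. When the screen often drops it, at 1 SD or less, the unadjusted excess is at most about 6 percentage points. This stands as far as it goes. A reader might infer that the p-value screen is the main fault here; the calculation does not bear that out. What the defence lacks is any text making birth size a candidate. The univariate correlation is also a planned result in its own right.

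Three further objections stand:

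- A reader might take the Introduction to say that SGA raises these hormones and that SGA infants are known to catch up faster. It reports only some evidence of higher levels, and calls the relation to catch-up growth not known. The SGA-growth link is therefore my assumption.
- A reader might extend the concern to every hormone. The cited evidence is for FSH and testosterone; testosterone is not assayed and LH is not mentioned.
- The shifts are assumed. Small ones give almost no inflation, and larger ones than those shown would give higher rates, but the documents support no particular value.

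The preliminary label limits how much the point matters, but does not answer it: the plan still tests at 0.05, and the title speaks of effects.

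**Conclusion.** The gap is real and narrow. The protocol identifies birth size as a possible correlate of FSH, admits SGA infants, and then leaves birth size out of the analysis of FSH and growth. The main defect is that omission. Confounding is possible rather than demonstrated, and the documents support it for FSH only.

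With 20-30% SGA infants, equal shifts in FSH and growth, and no hormone effect, the unadjusted false-positive rate is about 5-6% at 0.5 SD, 9-11% at 1 SD and 21-29% at 1.5 SD. It stays at about 5% if SGA does not affect growth. Forcing birth size in keeps it at about 5% in every scenario. The SGA share and the shifts are assumptions, so these figures show how far the result could be affected, not what to expect in this study.

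Severity is minor: the analysis serves a secondary objective of a self-described preliminary study.

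**What to change.** In Section 6, and in the matching synopsis text:

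- Pre-specify one continuous birth-size covariate: a weight-for-gestational-age z-score. State whether it uses birth weight or T1 weight, and name the growth reference.
- Enter it in the hormone-growth regression whatever its univariate p-value, exempt from both the screen and the backward elimination.
- Report the hormone-growth association with and without it.
- Report the number of SGA infants in each gestational-age group, beside the FSH comparison.

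A continuous score suits 20 infants better than a yes/no split, because SGA infants may be few. Birth size is fixed before the hormones are measured, so adjusting for it does not take away a true hormone effect on later growth.

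The cost is one degree of freedom: residual degrees of freedom fall from 20 − 2 = 18 to 20 − 3 = 17 in a model with one hormone term. No extra visit or sample is needed, since weight is recorded from T1 and gestational age is needed for eligibility. The plan does have to add the definition and the growth reference, and birth weight must be added as a variable if it is used in place of T1 weight.

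### The hormone-growth analysis has no age-standardised outcome, no adjustment for age or gestation and no rule for repeated visits, so correlating serial raw values can produce a link where none exists

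*Combined protocol and SAP*

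**What the plan says.** Section 2 sets the secondary objective: "Identify a link between hormone levels and linear growth in the first months of life in preterm neonates". The full title goes further and speaks of "EFFECTS ON CATCH-UP GROWTH AND NEUROCOGNITIVE OUTCOME IN MALE PRETERM NEONATES".

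Section 4.2 lists what is measured: "Auxological parameters for each evaluation will include: length, weight, head circumference". It adds testicular volume and position, and penile length. Neither section mentions an SDS, a growth reference, a velocity or a change over an interval.

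Section 4 sets the timing. Urine and clinical measures are taken at days 1-3, at day 7, weekly to 40 weeks post-conceptual age or discharge, and then at routine clinics to 12 months corrected age. The number and ages of the clinic visits are not given.

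Section 6, repeated in the synopsis, gives the method: "Pearson's correlation shall be used for univariate analysis of association of and multivariate analysis shall be performed using backward stepwise linear regression analysis". The candidate factors are those significant univariately at the 0.05 level. It also says "Some data may require log transformation", which does not remove an age trend. Age and gestational age are not named as covariates, and nothing says how several visits from one infant enter the analysis.

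**The concern.** Section 1 describes minipuberty as a surge: "gonadotropins levels have a peak at 3 months of life and a progressive exhaustion at around 6 months". Length rises throughout. Two quantities that both depend on age will correlate across visits whether or not one affects the other. The sign depends on which part of the surge the data cover: positive while hormones rise, negative once they fall.

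A second mechanism adds to this. Visits from one infant are not independent. A boy who is long for his age stays so, and a boy with high LH tends to stay so. Treating his visits as separate subjects overstates the information.

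At stake is whether the study can say that infants with higher hormone levels grow faster than expected for their age, which is what catch-up means. An analyst following Section 6 has serial lengths and serial hormone values and no instruction to remove age or to respect the infant as the unit. The genital measures are left in the same state.

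**Working it through.** **Plan's own figure.** The sample size of 20 (Section 3.1) comes with no effect size, SD or power, so there is nothing to reproduce.

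**Number of records.** The simulation below took gestational age as uniform from 24 to 32 weeks, which gives about 250 in-hospital records, or 250/20 = 12.5 per infant. Clinics were assumed at 46, 53, 66, 79 and 92 weeks post-conceptual age. Three clinics to 6 months corrected add 20 × 3 = 60 (310 records). Five to 12 months add 20 × 5 = 100 (350 records).

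**Effect on the significance threshold** (two-sided 0.05 assumed). The critical value is |r| = t/√(t² + n − 2).
- n = 20: t = 2.101, so 2.101/√(4.414 + 18) = 0.444.
- n = 200: 0.139. n = 300: 0.113.

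Pooling visits therefore cuts the threshold to about a quarter or a third, although there are still 20 infants.

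**Null simulation** (1,000 studies per scenario; length independent of hormone given age and gestational age). From the documents: 20 infants, the visit schedule, Pearson at 0.05. Assumed: log hormone rises, peaks at 4, 8 or 12 weeks of age and falls; log-amplitude 2 (0.8 as sensitivity); between-infant SD 0.4; residual SD 0.7; length SD about 2 cm; gestational-age effect on the hormone of 0 or 0.1 log units per week.

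| Analysis | Studies with p < 0.05 | Median r |
|---|---|---|
| Raw length, in-hospital visits pooled | 88-100% | +0.21 to +0.44 |
| Raw length, pooled to 6 months corrected | 3-100% | 0.00 to −0.28 |
| Raw length, pooled to 12 months corrected | 99-100% | −0.21 to −0.48 |
| Raw length, amplitude 0.8, peak 12 weeks, in-hospital or to 12 months | 74-75% | +0.18 or −0.14 |
| Length z-score, visits still pooled | 20-36% | about 0 |
| Mean z-score v mean hormone, one value per infant | 3.4-6.3% | not recorded |

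A separate null simulation on other assumed curves gave 10-100% overall for pooled raw length and 90-100% to 12 months. It gave 20-30% for pooled z-scores and 4-7% for one age-standardised value or change per infant.

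**Does the stepwise model rescue it?** Nothing in Section 6 forces age in. In a further null simulation (300 studies per scenario), adding linear postnatal age to the pooled regression still left a significant hormone term in 27-99% of studies, and adding gestational age as well left 15-100%. Both variables curve with age and visits cluster within infants, so linear adjustment is not enough.

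**One raw value per infant.** These results come from the first simulation, at log-amplitude 2.

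| Per-infant analysis | No gestational-age effect on hormone | 0.1 log units per week |
|---|---|---|
| One visit nearest 4 weeks of age | 4-6% | 14-16% |
| Mean raw length | 5-13% | 21-39% |
| Crude length velocity | 5-12% | 12-65% |

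The assumed gestational-age effect is large: 0.1 × 8 weeks = 0.8 log units from 24 to 32 weeks, twice the between-infant SD of 0.4. Some such effect is plausible, because Section 1 reports higher and longer-lasting levels in preterm than in term infants, and a primary objective compares levels below 28 weeks with those at 28-32.

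**What 20 infants can show** (Fisher's z).
- r for 80% power: tanh[(1.960 + 0.842)/√17] = tanh(0.680) = 0.59.
- Power at r = 0.5: Φ(0.549 × √17 − 1.960) = Φ(0.305) = 62%.
- 95% interval around an observed 0.5: tanh(0.549 ± 1.960/√17) = 0.07 to 0.77.

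**The case against.** The strongest reply is that the plan never says raw length will be analysed or that visits will be pooled. Section 4.2 lists measurements, and length is also the input to velocity or an SDS. The wording of the objective and the title points towards change rather than attained size. In the text available, the Pearson sentence does not name its variables; since words may have been lost there, nothing here rests on that gap. This reply stands: the defect is an unspecified analysis, not a wrongly specified one.

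A reader might therefore infer too much, namely that the plan analyses raw length and that a spurious link is bound to appear. The documents do not support that. One record per infant near a fixed age is close to nominal unless gestational age drives the hormone. Pooling to 6 months can cancel to nothing. In-hospital false positives were only 12-31% in one set of assumed curves with a 4-week peak.

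It is also fair that the 3-month peak in Section 1 describes minipuberty in general. Timing in these preterm boys is what the primary objective sets out to find, so any peak age used here is an assumption. The objective's reference to early months also makes the 12-month window only one possible reading.

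What does not stand is that the omission is harmless. Two analysts could both follow Section 6, choose different windows, and report links of opposite sign from the same null data.

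**Conclusion.** The concern holds as a gap in specification with a real consequence. The plan gives no age-standardised growth outcome, no adjustment for age or gestational age, and no unit of analysis for repeated visits. If serial raw values are correlated across visits, a significant correlation of either sign can arise without any true link. That occurred in about 10-100% of null studies depending on window and peak timing (3% at the extreme), and in 90-100% to 12 months corrected age, falling to about 75% with a smaller hormone amplitude. Age standardisation alone is not a cure, since pooled z-scores still leave about 20-36%. One age-standardised value per infant restores the nominal rate.

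All percentages rest on assumed curves, SDs and clinic ages; only direction and order of magnitude should be relied on. The z-scores were also computed against the true simulated age curve, which no real reference will match exactly. The objectives affected are secondary, but the title rests on them, so the change should be made before analysis.

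**What to change.** In Section 6, replace correlation of raw values with the following.

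- **Growth outcome:** one primary value per infant, the change in length SDS (named preterm and infant reference, corrected age) from birth to the last in-hospital measurement at or before 40 weeks. Change to the clinic visit nearest a stated corrected age, within a stated window, is supportive.
- **Hormone summary:** one per infant over the same or an earlier period, for example time-averaged log LH, with FSH secondary.
- **Model:** linear regression with gestational age forced in, not selected by a univariate screen. Alternatively, use a mixed model on all visits with a random infant effect, a flexible age term and gestational age.
- **Penile length and testicular volume:** the infant-level slope or the age-adjusted mixed model. Reference SDS for these measures cannot be assumed to be available.
- **Reporting:** exploratory, with estimates and confidence intervals. Naming one primary growth outcome and one primary hormone avoids a set of interval-by-hormone tests in 20 infants.

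**Cost.** No new measurements are needed: length, visit timing, sex and gestation already arise from the study. A growth reference and a visit-window rule must be chosen, because clinic ages are not fixed and weekly sampling may stop at discharge. The in-hospital interval will differ between infants (up to 16 weeks from 24 weeks' gestation, 8 from 32), so its length should be reported. Precision will be low with 20 infants.
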